### **7.3. Assigning Causal Relationship to Study Drug**

The reasonable possibility of the relationship of an adverse event to study drug(s) is to be assessed with careful medical consideration at the time of evaluation of an adverse event. The following definitions are to be used for the relationship of the adverse event to study drug:

- **Probably related:** A clinical event, including laboratory test abnormality, with a reasonable time sequence to administration of the drug, unlikely attributed to concurrent disease or other drugs or chemicals, and that follows a clinically reasonable response on re-administration (rechallenge) or withdrawal (dechallenge).
- **Possibly related:** A clinical event, including laboratory test abnormality, with a reasonable time sequence to administration of the drug but that could also be explained by concurrent disease or other drugs or chemicals. Information on drug withdrawal may be lacking or unclear.
- **Not related:** A clinical event, including laboratory test abnormality, with a temporal relationship to drug administration that makes a causal relationship improbable and/or in which other drugs, chemicals, or underlying disease provide a plausible explanation.

All adverse events, whether or not related to study drug, must be fully and completely documented on the adverse event page of the eCRF and in the patient's clinical record. In the event a patient is withdrawn from the study because of an adverse event, it must be recorded on the eCRF as such.

#### 7.4. Assigning Severity Rating for Adverse Events

Severity describes the intensity of a specific event (as in mild, moderate, or severe myocardial infarction); the event itself, however, may be of relatively minor medical significance, such as a severe headache. This is not the same as "serious," which is based on patient/event outcome or action taken.

The investigator must determine the severity of each adverse event according to the National Cancer Institute CTCAE. For terms not specified with the CTCAE, the criteria in [Table 7-1](#) should be used to determine the grade severity.

**Table 7-1 Criteria for Determining the Grade/Severity of Adverse Event Terms Not Specified by the National Cancer Institute CTCAE**

Grade	Criteria
1/Mild	Asymptomatic or mild symptoms, clinical or diagnostic observations only; intervention not indicated
2/Moderate	Minimal, local, or noninvasive intervention indicated; limiting age-appropriate instrumental activities of daily living
3/Severe or medically significant	Not immediately life-threatening; hospitalization or prolongation of hospitalization indicated; disabling; limiting self-care activities of daily living
4/Life-threatening	Life-threatening consequences; urgent intervention indicated
5/Death	Death related to adverse event

CTCAE = Common Terminology Criteria for Adverse Events.

Adverse event severity should be recorded in the appropriate section of the adverse event case report form and in the patient's source documents.

## 7.5. Adverse Events of Clinical Interest Reporting

Adverse events of clinical interest in this study are defined as any increase in ALT or AST  $\geq 3 \times$  ULN.

Any ALT or AST elevation of this degree or greater occurring during the Open-Label Treatment Period or the Follow-Up visit should be reported to the sponsor using the Safety Report Form **within 24 hours of the study site personnel's knowledge of the event** (see Section 7.6), **even if the event does not meet serious adverse event criteria**. Additional instructions for evaluating patients with an increase in ALT or AST  $\geq 3 \times$  ULN may be found in [Appendix 7](#).

### 7.5.1. Criteria for Temporary Withholding of Study Drug in Association with Liver Test Abnormalities

Hepatic enzymes will be monitored in accordance with FDA drug-induced liver injury guidelines [[FDA, 2009](#)].

If the following liver test abnormalities develop, study drug should be withheld immediately with appropriate clinical follow-up (including repeat laboratory tests, until a patient's laboratory profile has returned to normal/baseline status), and the event reported as a serious adverse event:

- ALT or AST  $> 8 \times$  ULN; or
- ALT or AST  $> 5 \times$  ULN and persists for more than 2 weeks; or
- ALT or AST  $> 3 \times$  ULN **and** total bilirubin  $> 2 \times$  ULN **or** the INR  $> 1.5$ ; or
- ALT or AST  $> 3 \times$  ULN with appearance of fatigue, nausea, vomiting, right upper quadrant pain or tenderness, fever, rash and/or eosinophilia ( $> 5\%$ ).

Rechallenge may be considered if an alternative cause for the abnormal liver tests (ALT, AST, total bilirubin) is discovered and the laboratory abnormalities resolve to normal or baseline values. The investigator and sponsor must discuss and agree with any decision to rechallenge.

Rechallenge should not occur when the etiology of the liver test abnormalities is considered possibly drug induced.

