#### **4.5. Removal of Patients from Therapy**

Completion of the Week 104 visit defines completion of the study. Patients may withdraw consent to participate in the study and discontinue treatment at any time for any reason. Investigators or the medical monitor may remove patients from therapy under this protocol for reasons of safety and/or lack of compliance as discussed below. Patients removed from therapy for any reason will undergo the assessments for the Early Termination visit (see the Week 104 visit on the Schedule of Activities, Section 1.1) and will have a Follow-up visit to assess safety approximately 30 days after the end of study drug treatment (ie, after the patient's last dose of study medication). When patients complete the study or early terminate from the study, they must be deactivated from the study in the interactive voice response system/interactive web response system (IVRS/IWRS), eDiary, and tablet device.

The following safety and/or compliance events will result in the removal of patients from therapy either permanently or until the etiology of the problem has been identified and resolved:

- Any adverse event that is intolerable to the patient and that cannot be ameliorated by the use of adequate medical intervention, or that in the opinion of the investigator or medical monitor would lead to undue risk to the patient if dosing continued;
- If it is discovered after enrollment that a patient failed to meet protocol entry criteria and continued participation poses an unacceptable risk to the patient's health;
- If the following liver test abnormalities develop, study drug should be discontinued immediately with appropriate clinical follow-up (including repeat laboratory tests, until a patient's laboratory profile has returned to normal/baseline status):
  - ALT or AST > 8 x ULN; or
  - ALT or AST > 5 x ULN and persists for more than 2 weeks; or
  - ALT or AST > 3 x ULN in conjunction with elevated total bilirubin > 2 x ULN or international normalized ratio (INR) > 1.5; or
  - ALT or AST > 3 x ULN with appearance of fatigue, nausea, vomiting, right upper quadrant pain or tenderness, fever, rash and/or eosinophilia (> 5%);

- 
- QT interval by the Fridericia correction (QTcF) prolongation of more than 500 msec read by a cardiologist;
  - Evidence of endometrial hyperplasia or endometrial carcinoma on endometrial biopsy;

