### **5.5. Dose Reduction/Dose Administration**

No toxicity-related dose reductions of study drug are permitted. Patients who experience a grade 3 or greater toxicity that cannot be ameliorated by the use of adequate medical intervention should have their treatment interrupted until the toxicity improves to a grade 2 or lower severity. Patients may subsequently be re-started on study drug with the written approval of the sponsor (or designee).

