### 7.5.2. Criteria for Permanent Discontinuation of Study Drug in Association with Liver Test Abnormalities

Study drug treatment should be discontinued permanently if all of the following 4 criteria are met (ie, potential severe drug-induced liver injury/Hy's law case):

1. AST or ALT increases to  $\geq 3 \times$  ULN; AND
2. Total bilirubin increases to  $> 2 \times$  ULN or INR  $> 1.5$ ; AND
3. Alkaline phosphatase value does not reach  $2 \times$  ULN; AND
4. No alternative cause explains the combination of the above laboratory abnormalities; important alternative causes include, but are not limited to the following:
  - Hepatobiliary tract disease;
  - Viral hepatitis (eg, hepatitis A/B/C/D/E, Epstein-Barr virus);

- Exposure to hepatotoxic agents/drugs or hepatotoxins, including herbal and dietary supplements, plants, and mushrooms;
- Alcoholic hepatitis;
- Nonalcoholic steatohepatitis;
- Autoimmune hepatitis.

If an alternative cause for hepatotoxicity is identified, then it should be determined (based on the severity of the hepatotoxicity or event) whether study drug treatment should be withheld or permanently discontinued as appropriate for the safety of the patient.

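### Sections 4.5 and 7.5.1 give different actions and resumption conditions for the same four liver triggers, Section 5.5 overlaps with a looser restart rule, and no precedence is stated

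*Protocol*

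**What the plan says.** Section 4.5 lists events that lead to "removal of patients from therapy either permanently or until the etiology of the problem has been identified and resolved". Its liver bullet says "If the following liver test abnormalities develop, study drug should be discontinued immediately with appropriate clinical follow-up" and gives four triggers, the first being "ALT or AST > 8 x ULN; or". The opening paragraph of the same section adds: "Patients removed from therapy for any reason will undergo the assessments for the Early Termination visit".

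Section 7.5.1, whose title concerns temporary withholding, repeats the four triggers, but there the drug is withheld and the event is reported as serious. Rechallenge may be considered if an alternative cause is found and "the laboratory abnormalities resolve to normal or baseline values". Investigator and sponsor must agree, and rechallenge should not take place when the abnormality is possibly drug induced. Appendix 7 also says withheld and points to Section 7.5.1.

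Section 5.5 covers toxicity of grade 3 or above that medical intervention cannot ameliorate. Treatment is interrupted until grade 2 or lower, and then: "Patients may subsequently be re-started on study drug with the written approval of the sponsor (or designee".

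Section 7.5.2 sets four joint criteria for permanent discontinuation. The first begins "AST or ALT increases to" and continues with ≥ 3 x ULN.

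**The concern.** A site that sees one of the four abnormalities can find its instructions in more than one section, and the sections do not agree on what to do or on when drug may be resumed.

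The action word has consequences. Under Section 4.5, removal for any reason brings Early Termination assessments. These include an endometrial biopsy unless an exception in Section 6.3 applies and, from Week 36, a DXA scan unless one was done in the previous six weeks (Section 6.5.2.6). Section 7.5.1 describes a pause with possible rechallenge and mentions no such visit. The primary endpoints are read at Week 52/Early Termination and Week 104/Early Termination, and Section 9.5 summarises discontinuations due to adverse events. How a held patient is classified can therefore reach both efficacy and safety tables.

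The resumption rule matters more. Section 7.10 names hepatic enzyme increase as a potential risk. One section would let drug be restarted in circumstances where another would not, and the protocol does not say which section governs.

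**Working it through.** No arithmetic applies. The check is a comparison of the texts.

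**Triggers.** All four match between Sections 4.5 and 7.5.1: ALT or AST > 8 x ULN; > 5 x ULN for more than 2 weeks; > 3 x ULN with bilirubin > 2 x ULN or INR > 1.5; > 3 x ULN with the listed symptoms, rash or eosinophilia.

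**Action and resumption.**

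| | Section 4.5 | Section 7.5.1 | Section 5.5 |
|---|---|---|---|
| Attached to the four triggers | Yes | Yes | No; general rule |
| Action | Discontinued (stem: permanent or temporary) | Withheld | Interrupted |
| Cause | Identified and resolved | Alternative cause found; no rechallenge if possibly drug induced | Not mentioned |
| Recovery level | None stated | Normal or baseline | Grade 2 or lower |
| Sponsor role in resuming | None stated in the stem | Must agree with investigator | Written approval |

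**Does Section 5.5 reach liver tests?** Under Section 7.1.1, a laboratory abnormality judged clinically significant because it requires drug interruption is an adverse event. Section 7.4 grades adverse events by CTCAE, and Section 9.5 assigns CTCAE toxicity grades to laboratory values. A liver abnormality of grade 3 or greater that cannot be ameliorated therefore falls within Section 5.5 as well as 7.5.1. Section 5.5 neither excludes liver tests nor refers to 7.5.1.

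**Where the rules agree and diverge.**

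1. Alternative cause found and resolved, tests back to baseline: the conditions in 4.5 and 7.5.1 are both met.
2. Drug identified as the cause, abnormality resolved off drug: the 4.5 stem can be read as satisfied; 7.5.1 says no rechallenge.
3. Alternative cause found, toxicity down to grade 2 but still above baseline: 5.5, where it applies, allows restart with sponsor approval; the 7.5.1 condition is not met.
4. No cause found, toxicity down to grade 2: 5.5, where it applies, allows restart with sponsor approval; neither the 4.5 stem nor the 7.5.1 condition is met.

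**Boundary at 3 x ULN.** Take ALT of exactly 3 x ULN, bilirubin > 2 x ULN, alkaline phosphatase below 2 x ULN and no alternative cause. Section 7.5.2 requires ≥ 3 x ULN, so all four of its criteria are met. The matching hold trigger in 7.5.1 and 4.5 requires > 3 x ULN and is not met. The other three triggers need > 8, > 5 and > 3 x ULN, so none of them is met either. Read literally, the permanent rule applies while no listed hold trigger does. The sign also differs in reporting: Section 7.5 uses ≥ 3 x ULN and Table 7-2 uses > 3 x ULN.

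**The case against.** The strongest reply is that the sections can be read together. The stem of Section 4.5 covers a mixed list of removal events, including QTcF prolongation, bone loss, noncompliance and pregnancy, and it allows temporary removal. Sections 7.5.1 and 7.5.2 then supply the liver detail and separate temporary from permanent. A site that satisfies 7.5.1 normally satisfies the 4.5 stem too. Section 5.5 is general and permissive, and a reader would ordinarily let a specific prohibition prevail over it. The sponsor must approve under 5.5 and agree under 7.5.1, so a restart that 7.5.1 advises against would need the sponsor's consent. At exactly 3 x ULN with raised bilirubin or INR, Appendix Table 1 calls for tests every 24 hours, Appendix 7 has drug withheld if close monitoring is not possible, and Section 4.5 allows removal for undue risk.

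Much of this stands, and it rules out several stronger readings that a reader might infer:

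- *That discontinued and withheld flatly contradict each other.* The 4.5 stem makes this ambiguity, not outright contradiction.
- *That three resumption conditions are set for the same four triggers.* Two are; the third reaches them only by overlap.
- *That 7.5.1 expressly bars rechallenge in every unexplained case.* Its stated bar covers possibly drug-induced abnormalities; an unexplained case simply fails the permissive condition.
- *That restart would be allowed at some particular enzyme multiple.* This depends on CTCAE cut-offs that the protocol does not print.

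The reply does not remove the gap. That the specific rule prevails is a convention the reader supplies; no section says so. The shared sponsor role limits unsupervised restarts but does not tell the sponsor which test to apply. Case 2 in the comparison diverges even without Section 5.5.

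**Conclusion.** The point holds as a partial inconsistency. The same four triggers carry different action words, with different stated consequences, and different resumption conditions. A general toxicity rule overlaps with them and, alone of the three, expressly allows restart with residual toxicity. Precedence is not stated. The inequality at 3 x ULN is a minor boundary mismatch.

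The documents give no expected rate of these abnormalities, so the number of patients cannot be derived; I assume it is small. The effect on the results should be slight, since the analyses are descriptive. The weight lies in patient safety and in uniform conduct across approximately 320 sites. The overlap with Section 5.5 rests on the protocol's own adverse event and grading sections. How many of the four triggers would be grade 3 or greater cannot be settled from the document.

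**What to change.** Reconcile Sections 4.5, 5.5, 7.5.1, 7.5.2 and Appendix 7 so that:

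- one action is stated for the four shared triggers, with a statement of whether a temporary hold calls for Early Termination assessments;
- the conditions for resuming drug agree;
- the inequality at 3 x ULN agrees between the hold and permanent-stop rules, with Section 7.5 and Table 7-2 aligned in the same pass;
- one sentence says which section takes precedence for liver test abnormalities, including how Section 5.5 relates to them.

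The sponsor decides which standard governs; none is proposed here. The cost is amendment wording, with no added tests or visits.

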### 7.5.2. Criteria for Permanent Discontinuation of Study Drug in Association with Liver Test Abnormalities

Study drug treatment should be discontinued permanently if all of the following 4 criteria are met (ie, potential severe drug-induced liver injury/Hy's law case):

1. AST or ALT increases to  $\geq 3 \times$  ULN; AND
2. Total bilirubin increases to  $> 2 \times$  ULN or INR  $> 1.5$ ; AND
3. Alkaline phosphatase value does not reach  $2 \times$  ULN; AND
4. No alternative cause explains the combination of the above laboratory abnormalities; important alternative causes include, but are not limited to the following:
  - Hepatobiliary tract disease;
  - Viral hepatitis (eg, hepatitis A/B/C/D/E, Epstein-Barr virus);

- Exposure to hepatotoxic agents/drugs or hepatotoxins, including herbal and dietary supplements, plants, and mushrooms;
- Alcoholic hepatitis;
- Nonalcoholic steatohepatitis;
- Autoimmune hepatitis.

If an alternative cause for hepatotoxicity is identified, then it should be determined (based on the severity of the hepatotoxicity or event) whether study drug treatment should be withheld or permanently discontinued as appropriate for the safety of the patient.

## 7.6. Serious Adverse Event Reporting

Using a Safety Report Form, all serious adverse events must be reported **within 24 hours of the study site personnel's knowledge of the event**, regardless of the investigator assessment of the relationship of the event to study drug.

The contact information for submission of serious adverse events, adverse events of clinical interest (defined in Section 7.5), and events of overdose is available on the Safety Report Form and is as follows:

**For questions on Serious Adverse Event/Adverse Event of Clinical Interest reporting, please call:**

- North/South America: PPD
- Europe, Asia-Pacific, and Africa: see region-specific phone numbers accompanying the Safety Report Form

The initial report should include:

- Study number (MVT-601-3103);
- Site address and number;
- Investigator name;
- Patient ID number, sex, and age;
- Details of study drug administration;
- The date of the report;
- A description of the serious adverse event (event term, seriousness of the event, date of onset, intensity);
- Causal relationship to the study drug.

If the patient died, the report should include the cause of death as the event term (with death as outcome) and whether or not the event leading to death was related to study drug treatment, as well as the autopsy findings if available.

Do not delay reporting a suspected serious adverse event in order to obtain additional information. Any additional information, if collected, can be reported as a follow-up to the initial report. All serious adverse events will be followed until resolution, until the event has stabilized, and/or reached a new baseline. All serious adverse events continuing at the completion of the study must be assessed or followed to determine outcome.

## 7.7. Study Drug Overdose Management

The medical monitor must be contacted in the event of any study drug overdose.

An overdose is defined as a known deliberate or accidental administration of study drug, to or by a study patient, at a dose above that assigned to that individual patient according to the study protocol.

For this study, any dose of relugolix > 80 mg within a 24-hour window is an overdose and any dose of estradiol/norethindrone acetate > 2 × the protocol dose is an overdose (ie, more than 2 capsules taken within a 24-hour window). There is no known antidote for an overdose.

In the event of an overdose, the investigator or treating physician should:

- Contact the medical monitor within 24 hours;
- Closely monitor the patient for adverse events and laboratory abnormalities;
- All overdose events are to be reported within 24 hours of awareness by the study site, using a Safety Report Form according to Section 7.6, whether or not the overdose is associated with an adverse event;
- Document the quantity of the excess dose as well as the duration of the overdosing in the eCRF.

The medical monitor, in consultation with the investigator, will make decisions regarding patient status and potential dose interruptions, based on the clinical evaluation of the patient.

## 7.8. Pregnancy Reporting

If any patient becomes pregnant during the study, the site must discontinue the patient from the study treatment immediately and have her return for an Early Termination visit.

If the patient agrees, the investigator should notify the patient's primary care physician of the pregnancy and provide details of the patient's participation in the study and treatment.

A pregnancy is to be reported to the sponsor within 24 hours of awareness by the study site personnel, using the Pregnancy reporting forms and contact information in Section 7.6. The expected date of delivery or expected date of the end of the pregnancy, last menstruation, estimated conception date, pregnancy result, and neonatal data, etc., should be included in this form, as available. Document the pregnancy in the eCRF as well.

The investigator will follow the medical status of the mother, as well as the fetus, and will report the outcome to the sponsor.

## 7.9. Vital Signs, Physical Examinations, Clinical Laboratory Tests, Electrocardiograms, and Bone Mineral Density Measures

Section 6.5.2 details the requirements for measurement of safety parameters including vital signs, physical examinations, clinical laboratory tests, ECGs, and bone mineral density.

## 7.10. Benefit/Risk Assessment

Adverse drug reactions (identified risks) associated with relugolix in women include nonserious events of hot flush, headache, hyperhidrosis, and loss of bone mineral density. In this protocol, relugolix will be evaluated for its benefit on endometriosis-associated pain. Low-dose hormonal add-back therapy with estradiol and norethindrone acetate will be evaluated for maintenance of bone mineral density during treatment with relugolix.

Potential risks that may be associated with relugolix treatment in women, based on nonclinical data and data available for similar compounds, include drug interactions, cardiovascular effects (corrected QT [QTc] prolongation), hepatic enzyme increases, phospholipidosis (PLD), reproductive toxicity, and metabolic and cardiovascular changes (insulin resistance, dyslipidemia, increased weight) with an increased risk of diabetes mellitus and possible increased risk of cardiovascular disease. Additionally, there are potential risks associated with the addition of estradiol/norethindrone acetate. Summaries of findings from both nonclinical and clinical studies conducted with relugolix can be found in the current version of the Investigator Brochure.

The risk assessment and mitigation strategy for this protocol are outlined in [Table 7-2](#).

